Three elements are needed to perform these cost and cost-effectiveness analyses: clinical outcomes, health care utilization data, and value data for assigning costs to utilization. The sources of information for these elements may be summarized as follows. Health outcomes will be determined from patient interviews. Health care utilization will be determined from national VA data systems and CSP study forms. Cost data will be extracted from national data systems when possible and from published sources or VA administrators as needed. The range of costs considered will include: direct inpatient and outpatient care costs; indirect costs for staff time; and direct and indirect costs associated with use of equipment and office space and with use of other physical and administrative resources.

A key component of the economic analysis is our strategy for estimating usual care costs in a comparison group representing "usual care." A customized imputation approach is required for this component, because the randomized trial does not include a "treatment as usual" study arm. Patients assigned to the trial's comparison or "placebo" group will receive sham rTMS. Sham treatment does not resemble usual care for treatment-resistant patients in the VA. Patients assigned to sham will attend up to 30 sham rTMS sessions (see **Figure 1**, "*Patient Flow in Study*"). Patients who do not achieve remission (HRSD<=10) after the first 20 sham rTMS sessions will attend additional sham rTMS sessions. Thus, the expected cost of usual care during the acute treatment phase of the trial, which will last from 4 to 11 weeks, must be imputed for all patients receiving sham rTMS. These imputed costs will be added together with actual costs during the follow-up phase to estimate the cost of usual care for treatment-resistant patients in the comparison group. We provide further details on the imputation method and related sensitivity analyses below.

Figure 1. Patient Flow in Study (in Main Proposal)

B. Objectives

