The short-term 24-week period was chosen to coincide with the collection of clinical endpoints at the end of the CSP 556 follow-up phase. The longer term 6- to 12-month period was chosen to maximize the opportunity to observe cost offsets from rTMS. The reason for specifying 6- to 12-months rather than a single time period is that due to extant data lags we do not know in advance how long of a retrospective period will be available to us, given the potential variability in the timing of patient recruitment. Maximization of sample size is paramount to accurate cost estimation. Therefore, we will select the longest 6- to 12-month post-treatment period that will allow us to include the largest sample of study participants. We believe that nearly all patients will have completed treatment and will have 6-months post-treatment cost data available before the end of the three-year study. A longer cost consequence follow-up will be pursued, if the extant data are available. Cost consequences

results will be discussed in terms of statistical significance and the magnitude and types of differences (e.g., inpatient and outpatient).

We will then estimate the cost-effectiveness of rTMS therapy in producing a sustained remission from depression (HRSD \leq 10) at 24-weeks post-treatment. We will report the incremental cost of rTMS per incremental remission, which will provide a standardized measure of the cost-effectiveness of rTMS therapy relative to that of “usual outpatient care”. These estimates will allow us to test a third hypothesis:

3. Relative to usual care, rTMS therapy for treatment-resistant depression is cost-effective in producing a sustained remission from acute depressive symptoms, in outpatients.

We will calculate a 95% confidence region for all estimated cost-effectiveness ratios. The ratios will be discussed in light of the cost-effectiveness of antidepressant medication and ECT. Estimates for these alternative therapies are available from published studies.^{3, 4}

C. Background

1. Prevalence

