We will estimate the average cost differences between active-rTMS and usual care during the acute treatment phase and the follow-up phase. Two analyses will be conducted, one for the period extending 24-weeks post-treatment and one for the period extending 6- to 12-months post-treatment. Total average direct and indirect health care costs for all inpatient and outpatient care will be included in our estimates. Will also produce separate estimates by study phase (treatment or follow-up), in order to isolate any post-treatment cost-offset effects. We will

collect utilization and cost data from HERC, DSS Pharmacy, PBM, and National Patient Care Database (OPC and PTF) files for at least a 30-month period, starting one year prior to the date of randomization and extending one year after the end of the treatment follow-up phase. For patients randomized to sham-rTMS, we will assume that health care utilization and costs during the post-treatment phase are representative of usual health care utilization and costs for these patients. An imputation approach (described in the next paragraph) will be used to estimate their cost of usual care during the acute treatment phase.

Usual Care Costs for Patients Randomized to Sham rTMS. As noted earlier, usual daily cost values will be imputed for patients in the comparison group. Imputation is necessary because our cost analysis requires an estimate of the difference between the cost of providing rTMS intervention and the cost of providing “usual services over a similar period of potential intervention time”. This “incremental cost” cannot be estimated by the difference in average health care costs during the acute treatment phase between the active- and sham-rTMS treatment groups. The estimator for the average incremental cost of rTMS can be expressed as $E(C | T_a) - E(C | T_u)$, where C is health care cost, T_a indicates receipt of active rTMS and T_u indicates receipt of usual care. In randomized trials, estimates of the second component of this expression, $E(C | T_u)$, are normally calculated as the average cost of care in the comparison group. In this trial that approach is problematic, because this trial will not include a “usual care” group, and the sham-rTMS group will potentially get protocol-driven additional days of care as compared to the active-rTMS group, if the latter is more effective.

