The remission outcomes data – where a sustained remission is defined as HRSD \leq 10 at 6-weeks post-treatment – will be used in conjunction with incremental treatment cost estimates to determine an incremental cost-effectiveness ratio (ICER) for the intervention. The resulting ICER will represent the estimated incremental cost per sustained remission, measured at 6-weeks post-treatment. The ratio will be expressed as: $ICER = [E(C | T_a) - E(C | T_u)] / [P(R | T_a) - P(R | T_u)]$, the difference in average acute treatment costs divided by the difference in probability of remission (R) between the two groups. Note that this assumes that the P(R) among patients receiving sham-rTMS is approximately equal to the probability of remission among usual care patients. A 95% confidence region surrounding cost-effectiveness ratios will be estimated using bootstrapping methods.¹⁷⁻¹⁹

The cost-effectiveness analysis could produce one of three major results: (1) rTMS may be cost neutral or less expensive and also more effective than usual depression care, indicating that its implementation is highly desirable; (2) rTMS might not be shown clinically effective in the VA, in which case its relative cost impact is irrelevant to VA decision-makers; (3) rTMS therapy will be more expensive than sham but will yield a greater likelihood of sustained remission. In this last case, the costs of a sustained remission will be compared with the cost of the main alternative treatment option, namely ECT. Estimates of ECT costs will be derived from the literature and from VA administrative sources.⁴

5. Sensitivity Analyses

We will test the sensitivity of our results to a number of assumptions. At a minimum, we expect them to include:

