Discount and Inflation Rates. Costs incurred in earlier years must be inflated over time to maintain a steady level of purchasing power. They must also be inflated over time to reflect the discount rate, the rate at which people value money today over the same amount of money next year. The inflation rate, which we will measure by changes in the Consumer Price Index (CPI), could be varied in two ways for a sensitivity analysis. One is to use an alternative inflation measure, such as changes in the Gross Domestic Product Implicit Price deflator. We will use the CPI for main analyses and the Gross Domestic Product Implicit Price Deflator in the sensitivity analysis. A second approach is to vary the CPI by a small percentage, such as +/- 1.0% per year. Likewise, we will vary the assumed 3% discount rate by using alternative rates, such as 2% or 5%.

Usual Cost of Care. We will test our assumption that our imputed average costs in usual care for patients randomized to sham-rTMS are typical of treatment-resistant patients with major depression by comparing our average costs estimates for this group to a similar group of VA patients who are not participating in CSP 556. We will use Austin OPC-file data patients who were screened for participation in the study to estimate a propensity score for treatment-resistance among patients with a major depression diagnosis. The propensity score predictors will include an algorithm for possible treatment-resistance, which will be based on ICD-9 codes, number of changes in antidepressant medications in the past 12 months, treatment with a mood stabilizer, receipt of ECT, and other factors identified in extant studies.^{6, 7, 9, 10} Using this propensity score metric, we will identify treatment-resistant likely patients in the VA, and estimate their average health care costs and the variance of costs. Statistics for mean and variance will be compared with analogous sample parameters for patients randomized to sham. Based on these comparisons, we will define sensitivity ranges and apply them to our cost-effectiveness and cost-consequences estimates.

6. Power Analysis.

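### The cost-effectiveness ratio is stated against usual care, but its remission difference is rTMS versus sham, and no listed sensitivity analysis tests the assumption that joins the two

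*Protocol*

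**What the plan says.** The target is usual care throughout. Hypothesis 3 (Appendix M, section B) reads "Relative to usual care, rTMS therapy for treatment-resistant depression is cost-effective in producing a sustained remission from acute depressive symptoms, in outpatients". Section D.3 defines the cost estimator so that "T_u indicates receipt of usual care", and D.4 carries the same symbol into the ICER, described as "the difference in average acute treatment costs divided by the difference in probability of remission (R) between the two groups".

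The appendix is open that no such arm exists. D.3 says "this trial will not include a “usual care” group", and section A says "Sham treatment does not resemble usual care for treatment-resistant patients in the VA", pointing to the number of sham sessions patients attend. For that reason acute-phase costs in the sham arm are replaced by an imputed figure: each patient's average daily VA cost over the six months before recruitment, multiplied by the average length of acute treatment in the active arm.

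For remission, D.4 uses the sham arm directly and notes that this "assumes that the P(R) among patients receiving sham-rTMS is approximately equal to the probability of remission among usual care patients".

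D.5 lists two sensitivity analyses: discount and inflation rates, and the usual cost of care. The second begins "We will test our assumption that our imputed average costs in usual care for patients randomized to sham-rTMS are typical", and ends "Based on these comparisons, we will define sensitivity ranges and apply them to our cost-effectiveness and cost-consequences estimates". Elsewhere, D.1 substitutes DSS for HERC costs and D.3 repeats the analyses without patients who died. D.4 specifies a bootstrapped 95% confidence region for the ratio.

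**The concern.** Within one ratio, sham is treated as unlike usual care for cost and as equivalent to it for outcome. The feature used to reject sham on the cost side is attendance at up to 30 sessions, and that could plausibly affect remission too. The possible outcomes in D.4 show the same mixture: the first sets rTMS against usual depression care, the third against sham.

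What is at stake is the meaning of the result. The appendix says its purpose is to inform VA managers deciding whether to invest in rTMS, including how far depressive symptoms improve compared with standard care. If the plan is followed as written, they receive a usual-care claim whose effect side was measured against something else, with no indication of how far the claim depends on treating the two as equal. A ratio with a small remission difference in its denominator is very sensitive to this.

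**Working it through.** The appendix states no ICER value, and D.6 declines to give a power analysis, so there is no figure of the plan's own to reproduce. The check has two parts.

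**1. Which comparator feeds each term**

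| Term | Stated comparator | Source of data | Listed sensitivity analysis |
|---|---|---|---|
| Acute-phase cost, comparison side | Usual care | Imputed from pre-recruitment VA costs (D.3) | Yes: outside cohort, ranges from mean and variance of costs (D.5) |
| Remission, comparison side | Usual care | Sham arm, by assumption (D.4) | None |

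The D.5 ranges are carried into the cost-effectiveness estimates, but they are built from costs and so move only the numerator. The analyses without deceased patients and the DSS analysis do not replace sham remission with a usual-care value either. The bootstrap resamples trial patients, so it covers sampling error in the sham remission rate, not a gap between sham and usual care.

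**2. How far the ratio moves**

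Write Pa for remission on active rTMS, Ps for sham, Pu for usual care, and ΔC for the cost difference, held fixed.

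- Planned ICER = ΔC / (Pa − Ps)
- ICER against usual care = ΔC / (Pa − Pu)
- Multiple of the planned value = (Pa − Ps) / (Pa − Pu)

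Inputs: Pa = 9% and Ps = 6%, from the 2008 meta-analysis summarised in the Investigator's Brochure (Appendix G). These are an illustration, not a forecast for this trial. Appendix M gives no usual-care remission rate, so Pu is assumed and varied.

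| Assumed Pu | Pa − Pu | Multiple of planned ICER |
|---|---|---|
| 3% | 0.06 | 0.03 / 0.06 = 0.50 |
| 4% | 0.05 | 0.03 / 0.05 = 0.60 |
| 5% | 0.04 | 0.03 / 0.04 = 0.75 |
| 6% (the plan's assumption) | 0.03 | 1.00 |
| 7% | 0.02 | 0.03 / 0.02 = 1.50 |
| 8% | 0.01 | 0.03 / 0.01 = 3.00 |
| 9% | 0 | undefined |

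The movement is smaller when the treatment difference is wider. With the same meta-analysis's response rates (25% v 17%, used only to show a larger gap), Pu two points below sham gives 0.08 / 0.10 = 0.80, and three points above gives 0.08 / 0.05 = 1.60.

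Direction, for positive ΔC and Pu below Pa: if Pu is below Ps, the planned denominator is too small and the planned ICER too high, so a finding in favour of rTMS would be conservative. If Pu is above Ps, the planned ICER is too low and flatters rTMS.

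A separate matter is that section B places sustained remission at 24 weeks post-treatment and D.4 at 6 weeks. The argument here is the same for either time point.

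**The case against.** The strongest reply is that nothing is hidden. D.4 states the assumption beside the formula, and D.3 says there is no usual-care arm. This stands, and it rules out one reading a reader might reach, that hypothesis 3 goes unanswered. It is answered, conditionally on a disclosed assumption.

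Second, the sentence in section A about sham not resembling usual care sits in an argument about visits and costs. Extending it to remission is an inference, not a contradiction in the text. This stands as well. The inference is reasonable because the stated reason is the number of sessions attended, but the appendix does not draw it.

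Third, the sham arm may be a fair proxy. The Risk Minimization section of Appendix G lets patients keep their outpatient clinician and their medication, apart from drugs that raise seizure risk. Sham is then closer to usual care plus sham contact, its remission may equal or exceed that of usual care, and any error would run against rTMS. That is plausible, but the documents do not establish it. A reader might argue the reverse, that stopping study treatment for a major medication change holds sham remission down. That provision is tied to dropping out of outpatient care or imminent suicidality, so it supports the argument only weakly.

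Fourth, D.5 introduces its list as a minimum, so further analyses are possible. Granted; the point is confined to what is listed. The main body of the protocol was not available for this check.

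Finally, a reader might infer that the plan offers only a single figure, or that the ratio is uncertain by an order of magnitude. The plan does provide a bootstrap region and cost ranges. A very large span arises only by pushing the assumed usual-care rate to extremes, using rates from studies that mostly followed patients for one to three weeks.

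**Conclusion.** The point holds in a limited form. The ICER combines a cost difference against imputed usual care with a remission difference against sham. Hypothesis 3 therefore depends on sham and usual-care remission being about equal. That assumption is disclosed, sits awkwardly with the appendix's own reason for imputing costs, and is not tested by any listed analysis.

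The size in this trial is unknown. The illustration (0.5 to 3 times the planned ICER for assumed usual-care remission of 3% to 8%) rests on short-term meta-analysis rates, a fixed cost difference and an assumed range. It shows that a departure of two or three percentage points can matter when the remission difference is small. It does not show that the planned ICER is wrong by that amount, or in which direction.

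This is a secondary economic analysis and the clinical conclusions are unaffected. The change is still worth making, because it alters what can be claimed relative to usual care at almost no cost.

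**What to change.** - In D.4 and hypothesis 3, describe the trial-based effect as rTMS versus sham, and use the same comparator consistently in the list of possible results.
- In D.5, add a sensitivity analysis that recomputes the ICER with usual-care remission varied on both sides of the observed sham rate. Keep the range below the active rate, where the denominator would reach zero.
- Report the usual-care remission rate at which the cost-effectiveness conclusion changes. For a positive cost difference ΔC and a benchmark cost per remission λ, the formula above gives Pu* = Pa − ΔC / λ. The appendix already names ECT as the alternative against which a dearer but more effective rTMS would be judged; the benchmark used should be stated.
- Qualify any statement relative to usual care by that threshold.

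The cost is a few lines of wording and one extra table, with no new data. The downside is that the usual-care claim becomes a range with a threshold. That fits D.6, which presents bounds on cost offsets as a main product of the economic study.

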In a meta-analysis by Burt et al. of 23 published comparisons for controlled rTMS prefrontal antidepressant trials containing both treatment-resistant and non-treatment-resistant subjects, the authors found that rTMS had a combined effect size of 0.67, considered to be a moderate to large antidepressant effect³². In a sub-analysis, rTMS was compared with ECT. The effect size for rTMS in these studies was greater than in the studies comparing rTMS to sham, which may indicate a participant selection bias. The authors infer that rTMS may be most effective in the patients who also satisfy clinical predictors for positive ECT response.

A meta-analysis conducted using the Cochrane library guidelines was performed using literature published prior to 2001⁴². This stringent meta-analysis included 14 trials suitable for analysis and found that left prefrontal high-frequency rTMS at two weeks produced significantly greater improvements in the Hamilton Rating Scale than did sham treatment. However, a comparison of rTMS in general (i.e., not limited to high-frequency left prefrontal treatment) did not show a statistically significant difference.

A 2008 meta-analysis by Lam and colleagues⁴³ evaluated 24 randomized, sham-controlled studies containing 1092 patients with treatment-resistant depression. The analysis found a standardized mean difference of 0.48 for rTMS. Active treatment produced a response rate of 25% and remission rate of 9% compared to 17% and 6% respectively for placebo. The effect was robust and very few patients withdrew from the trial for adverse effects (2% withdrawal rate for active, 1.5% for placebo). However, most studies evaluated had a short follow-up time of 1-3 weeks, with no studies that evaluated response beyond 9 weeks. We hope that the current study can answer questions about long-term response.

Side Effects and Complications

Routine rTMS is usually mildly uncomfortable, but in some cases, particularly when applied over certain peripheral or cranial nerves, the treatment can be painful. TMS treatment produces a sensation on the head that most patients tolerate without problems. The painfulness is linked to the intensity of stimulation, which varies from subject to subject because dosing is based on individual patients' motor thresholds. Thus, some patients with high motor thresholds receive higher dose TMS than do other patients, and there

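### Hypothesis 3 has no decision rule when rTMS is dearer and more effective, and a bootstrap region on the ratio scale may be hard to interpret

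*Protocol*

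**What the plan says.** Appendix M, section D.4, defines the incremental cost-effectiveness ratio (ICER) as "the difference in average acute treatment costs divided by the difference in probability of remission (R) between the two groups". Uncertainty is attached to that ratio: "A 95% confidence region surrounding cost-effectiveness ratios will be estimated using bootstrapping methods". Section B (Objectives) makes this general: "We will calculate a 95% confidence region for all estimated cost-effectiveness ratios".

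Section B also announces "These estimates will allow us to test a third hypothesis", namely that, relative to usual care, "rTMS therapy for treatment-resistant depression is cost-effective in producing a sustained remission from acute depressive symptoms, in outpatients".

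Section D.4 then lists three possible results:

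1. rTMS is cost neutral or cheaper, and more effective. Adoption is then highly desirable.
2. rTMS is not shown to be clinically effective. Its cost is then of no interest to decision-makers.
3. rTMS is dearer and more effective. Then "the costs of a sustained remission will be compared with the cost of the main alternative treatment option, namely ECT".

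Section B adds a looser benchmark: "The ratios will be discussed in light of the cost-effectiveness of antidepressant medication and ECT". No value per remission, margin or decision rule is given in the part of the protocol shown.

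**The concern.** Two things look wrong.

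First, a claim that a dearer and more effective treatment is cost-effective is true or false only against some stated value of a remission. The plan announces a test but gives no such value for result 3. A reader given the ratio and its region could argue the hypothesis either way.

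Second, the ratio behaves poorly as a scale for inference. Its denominator, the remission difference, is not restricted in sign. The numerator is not either: section B says that the direction of the cost effect cannot be known in advance, and hypotheses 1 and 2 predict savings. If the bootstrap replicates spread over more than one quadrant of the cost-effectiveness plane, the same ratio stands for opposite conclusions, and replicates with a denominator near zero give extreme values.

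At stake is whether VA managers, for whom the appendix says the analysis is intended, receive a statement on cost-effectiveness that follows from a rule fixed in advance.

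**Working it through.** The plan gives no sample size, power or threshold for the economic analysis, so there is no figure of its own to reproduce. Three checks were made.

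**1. Does each result have a criterion?**

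- Result 1 is dominance (or equal cost with more effect) and needs no threshold.
- Result 2 sets the cost question aside.
- Result 3 needs a threshold. Section D.4 compares cost per remission with the cost of a treatment, which is a different quantity. Section B offers only a discussion beside the cost-effectiveness of other treatments. Neither states a figure or a rule.

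To see how far the answer depends on the missing value, take incremental net monetary benefit, NMB = lambda × (remission difference) − (cost difference), where lambda is the value of one remission. Assumed inputs: 9% versus 6% remission (Appendix G, see check 3), 100 per arm, cost difference 5,000 with standard error 1,500. The arm size and both cost figures are assumptions. The limits and probabilities come from 200,000 simulated draws.

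| lambda | expected NMB | 95% limits | P(NMB > 0) |
|---|---|---|---|
| 10,000 | 10,000 × 0.03 − 5,000 = −4,700 | −7,727 to −1,676 | 0.001 |
| 100,000 | 100,000 × 0.03 − 5,000 = −2,000 | −9,806 to 5,942 | 0.31 |
| 400,000 | 400,000 × 0.03 − 5,000 = 7,000 | −22,021 to 36,613 | 0.68 |

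The same data point away from or towards cost-effectiveness according to lambda alone. The limits are finite at each lambda.

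**2. Does the sign of the ratio identify the result?**

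- Dearer and better: 5,000 / 0.03 = 166,667. Cheaper and worse: −5,000 / −0.03 = 166,667.
- Cheaper and better (dominant): −5,000 / 0.03 = −166,667. Dearer and worse (dominated): 5,000 / −0.03 = −166,667.

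So neither a positive nor a negative ratio can be read without knowing the quadrant. The favourable result 1, when it brings savings, has a negative ratio, as does the worst outcome.

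**3. How often could the denominator be at or below zero?** Appendix G reports, from a meta-analysis: "Active treatment produced a response rate of 25% and remission rate of 9% compared to 17% and 6% respectively for placebo". Per-arm numbers are not shown, so 80 to 180 is assumed. By normal approximation, with SE = √[(pa(1−pa) + ps(1−ps))/n] and P(difference < 0) = Φ(−(pa−ps)/SE):

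- 9% versus 6%, n = 80: SE = √(0.1383/80) = 0.0416. P = Φ(−0.72) = 0.235; 95% interval −5.1 to +11.1 points.
- 9% versus 6%, n = 180: SE = √(0.1383/180) = 0.0277. P = Φ(−1.08) = 0.140; 95% interval −2.4 to +8.4 points.
- 25% versus 17% (response rates in the source, used only as a more favourable case): P = 0.106 at 80 and 0.031 at 180.

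Binomial draws, counting exact zeros as well, give the wider range:

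| Rates | 50 per arm | 100 | 200 |
|---|---|---|---|
| 9% vs 6% | 35% | 25% | 15% |
| 25% vs 17% | 19% | 9% | 3% |
| 20% vs 10% (assumed) | 10% | 3% | 0.3% |

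At 9% versus 6% and 100 per arm, 7.8% of draws have a denominator of exactly zero, where the ratio is undefined.

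**The case against.** The strongest reply is that section D.4 already handles much of this. Result 1 is dominance, result 2 drops the cost question when efficacy is not shown, and result 3 names a comparator. That stands for results 1 and 2. A reader might infer that hypothesis 3 cannot be tested at all, and the document does not support that. For result 3 the reply fails, because a comparator without a figure or a rule does not decide a hypothesis.

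The second reply is that instability arises mainly where result 2 applies. If the remission difference is significant at the two-sided 5% level, at most about 2.5% of draws of that same difference fall below zero. For a difference powered at 80% or 90%, the expected share is about 0.3% or 0.06%. This also stands, and it limits the point. It does not cover the numerator, whose sign the plan leaves open.

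Third, the illustrative rates may not describe this trial. The meta-analysis covers mostly studies with 1 to 3 weeks of follow-up. At 9% versus 6% with 80 to 180 per arm, power would be only about 11% to 19%, which fits badly with the statement in section D.6 that the clinical study has enough power for a difference in health outcomes. It would be wrong to infer that 14% to 24% of this trial's replicates will be negative.

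Fourth, a reader might infer that percentile limits of the ratios are planned. The text says only that a region will be bootstrapped. It could mean a joint region on the cost-effectiveness plane, and one of the references cited for the method is on net health benefit. Both statements nevertheless attach the region to the ratios, and the text does not adopt net benefit. The commitment also covers ratios only; cost differences are analysed on their own scale.

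Finally, bootstrap details may properly sit in an analysis plan, and section D.6 presents the economic results as informative whether or not they reach significance. That bears on severity. It does not remove the announced test that lacks a criterion.

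**Conclusion.** The point holds in a limited form. When rTMS is dearer and more effective, hypothesis 3 has no decision rule. This follows from the text alone, at any sample size. Separately, an interval on the ratio scale is hard to interpret if the replicates cross quadrants or the remission difference is near zero.

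The second part is a risk of unknown size, because arm size, planning remission rates and incremental cost are not in the part shown. The 24% to 14% figure rests on 9% versus 6% remission and an assumed 80 to 180 per arm, and should not be read as a forecast. With a clearly positive remission difference the denominator problem largely disappears, while the missing rule and the ambiguity of a negative ratio remain.

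Severity is modest: a secondary economic hypothesis is affected, and the clinical comparison is not.

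**What to change.** In Appendix M, sections B and D.4:

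- Keep the ICER as a point estimate and show the bootstrap replicates on the cost-effectiveness plane, so that the quadrant is visible.
- Base inference for hypothesis 3 on incremental net monetary benefit, lambda × remission difference − cost difference, with a bootstrap 95% confidence interval.
- State a range of lambda, anchored on the cost-per-remission figures for ECT and antidepressants that the plan already intends to use, and give an acceptability curve over that range.
- Define cost-effective as net benefit above zero at the stated lambda.

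This takes a few lines and uses the same data and the same bootstrap. The one real cost is having to name the lambda range in advance.
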